7. PLANNED ANALYSIS

Each of the three possible trial parts was planned to be analysed separately. Cohort 1 and cohort 2 of trial part 1 will be presented in one table, but the reference group will be stratified to R (Cohort 1) and R (Cohort 2).

Safety analysis (refer to [Section 7.8](#)) will be performed by [REDACTED] and will be presented in Sections 15.1 to 15.4 of the CTR and in Appendix 16.2 and 16.1.13.1.

Inferential statistical analyses of PK endpoints (refer to [Section 7.4](#) and [Section 7.5.2](#)) will also be performed by [REDACTED] and will be presented in Section 15.5 of the CTR and in Appendix 16.1.13.3.

Descriptive data analysis of PK endpoints and concentrations will be performed by the department of Translational Medicine and Clinical Pharmacology (TMCP) at BI and will be presented in Section 15.6 of the CTR and in Appendix 16.1.13.5.

The format of the listings and tables will follow the BI standards (see BI-KMED-BDS-HTG-0045 [\(8\)](#)) with the exception of those generated for PK-calculations following BI standards for PK/PD analysis [\(9\)](#).

The individual values of all subjects will be listed, sorted by treatment sequence, subject number and visit. The listings will be included in Appendix 16.2 of the CTR.

For end-of-text tables, the set of summary statistics for non-PK parameters is:

N	number non-missing observations
Mean	arithmetic mean
SD	standard deviation
Min	minimum
Median	median
Max	maximum

For analyte concentrations and PK parameters, the following descriptive statistics will additionally be calculated:

Nobs	number of observations
CV	arithmetic coefficient of variation
gMean	geometric mean
gCV	geometric coefficient of variation
P10	10th percentile
Q1	1st quartile
Q3	3rd quartile
P90	90th percentile

The data format for descriptive statistics of concentrations will be identical to the data format of the respective concentrations. The descriptive statistics of PK parameters will be calculated using the individual values with the number of decimal places as provided by the evaluation

program. Then the individual values as well as the descriptive statistics will be reported with three significant digits in the CTR.

Tabulations of frequencies for categorical data will include all possible categories available in the CRF and will display the number of observations in a category, as well as the percentage (%). Percentages will be rounded to one decimal place and will be based on all subjects in the respective subject set whether they have non-missing values or not. The category 'missing' will be displayed only if there are actually missing values.

Units of variables should be given in the titles or column/row descriptors in brackets (e.g. (mg)).

Exclusion of PK parameters

The ADS “ADPP” (PK parameters) contains column variables APEX and APEXCO indicating inclusion/exclusion (APEX) of a PK parameter and an analysis flag comment (APEXCO). All analyses based on the PKS will include parameters only if they are not flagged for exclusion, that is APEX is equal to “Included”.

Exclusion of PK concentrations

The ADS “ADPC” (PK concentrations per time-point or per time-interval) contains column variables ACEX and ACEXCO indicating inclusion/exclusion (ACEX) of a concentration and an analysis flag comment (ACEXCO). Exclusion of a concentration depends on the analysis flag comment ACEXCO. For example, if ACEXCO is set to ‘ALL CALC’, the value will be excluded for all types of analyses based on concentrations. If ACEXCO is set to ‘DESC STATS’ the value will be excluded from descriptive evaluations per planned time point/time interval. If ACEXCO contains the addition ‘TIME VIOLATION’ or ‘TIME DEVIATION’ the value can be used for further analyses based on actual times. If ACEXCO is set to ‘HALF LIFE’, the value will be excluded from half-life calculation (and, as a consequence, any calculation that relies on λ_z) only; the value is included for all other analyses.

Further details are given in *BI-KMED-TMCP-MAN-0014* “Noncompartmental Pharmacokinetic / Pharmacodynamic Analyses of Clinical Studies” ([7](#)) and *BI-KMED-TMCP-MAN-0010*: “Description of Analytical Transfer Files and PK/PD Data Files” ([10](#)).

7.1 DEMOGRAPHIC AND OTHER BASELINE CHARACTERISTICS

Only descriptive statistics are planned for this section of the report, based on the TS. The data will be summarised by treatment sequence and in total.

7.2 CONCOMITANT DISEASES AND MEDICATION

Frequency tables are planned for this section of the report, based on the TS.

Concomitant diseases will be coded using the coding system of the Medical Dictionary for Drug Regulatory Activities (MedDRA). Medications will be coded using the World Health Organization Drug Dictionary (WHO-DD). The coding version number will be displayed as a footnote in the respective output.

The diagnoses and medications will be listed. Subjects without any concomitant diagnoses or concomitant therapies will be marked with a “No” in the respective column.

The relevance of the concomitant therapies to the evaluation of PK will be decided no later than at the RPM.

7.3 TREATMENT COMPLIANCE

Section 4.3 of the CTP:

Compliance will be assured by administration of all trial medication in the study centre under supervision of the investigating physician or a designee. The measured plasma concentrations of trial medication will provide additional confirmation of compliance.

It is not intended to list the compliance separately. Any deviations from complete intake will be addressed in the RPM and described in the CTR.

7.4 PRIMARY ENDPOINTS

The relative bioavailability of several MR formulations of Nintedanib compared to Ofev® IR will be investigated on the basis of the primary PK endpoint AUC_{0-∞} (see [Section 5.1](#)).

Each of the crossover parts will be analysed separately.

7.4.1 Primary analysis of the primary endpoints

Section 7.3.1 of the CTP:

The statistical model used for the analysis of the primary endpoint will be an analysis of variance (ANOVA) model on the logarithmic scale. That is, the PK endpoints will be log-transformed (natural logarithm) prior to fitting the ANOVA model. This model will include effects accounting for the following sources of variation: sequence, subjects within sequences, period and treatment. The effect 'subjects within sequences' will be considered as random, whereas the other effects will be considered as fixed. The model is described by the following equation:

$$y_{ijkm} = \mu + \zeta_i + s_{im} + \pi_j + \tau_k + e_{ijkm}, \text{ where}$$

y_{ijkm} = logarithm of response measured on subject m in sequence i receiving treatment

k in period j ,

μ = the overall mean,

ζ_i = the i^{th} sequence effect, $i = 1, 2, (3)$,

s_{im} = the effect associated with the m^{th} subject in the i^{th} sequence,
 $m = 1, 2, \dots, n_i$

π_j = the j^{th} period effect, $j = 1, 2, (3)$,

τ_k = the k^{th} treatment effect, $k = 1, 2, (3)$,

e_{ijkm} = the random error associated with the m^{th} subject in sequence i who received treatment k in period j .

where $s_{im} \sim N(0, \sigma_B^2)$ i.i.d., $e_{ijkm} \sim N(0, \sigma_W^2)$ i.i.d. and s_{im} , e_{ijkm} are independent random variables.

Point estimates for the ratios of the geometric means (test/reference) for the primary endpoint (see [Section 5.1](#)) and their two-sided 90% confidence intervals (CIs) will be provided.

For each endpoint, the difference between the expected means for log(T)-log(R) will be estimated by the difference in the corresponding adjusted means (Least Squares Means). Additionally their two-sided 90% confidence intervals will be calculated based on the residual error from the ANOVA and quantiles from the t-distribution. These quantities will then be back-transformed to the original scale to provide the point estimate and 90% CIs for each endpoint.

The implementation for this analysis will be accomplished by using the CSD macros based on PKS. The following SAS code can be used:

```
PROC MIXED DATA=indata METHOD=REML;
  CLASS subject treatment sequence period;
  MODEL logpk = treatment sequence period / DDFM=KR;
  RANDOM subject(sequence);
  LSMEANS treatment / PDIFF CL ALPHA=0.1;
  RUN;
```

7.5 SECONDARY ENDPOINTS

The relative bioavailability of several MR formulations of Nintedanib compared to Ofev® IR will also be investigated on the basis of the secondary PK endpoint AUC_{0-tz}, C_{max} and C₂₄ (see [Section 5.2.2](#)).

Each of the crossover parts will be analysed separately.

7.5.1 Key secondary endpoints

This section is not applicable, as no key secondary endpoint has been specified in the protocol.

7.5.2 (Other) Secondary endpoints

Section 7.3.2 of the CTP:

The secondary endpoints (refer to [Section 5.2.2](#)) will be calculated according to the relevant internal BI procedures and will be assessed statistically using the same methods as described for the primary endpoint.

7.7 EXTENT OF EXPOSURE

Descriptive statistics are planned for this section of the report based on the TS. The date and time of drug administration will be listed for each subject.

7.8 SAFETY ANALYSIS

All safety analyses will be performed on the TS.

The safety data for treated subjects who failed to complete the study (dropouts or withdrawals) will be reported as far as their data are available. All withdrawals will be documented and the reason for withdrawal recorded.

7.8.1 Adverse Events

AEs will be coded using MedDRA. The coding version number will be displayed as a footnote in the respective output.

Unless otherwise specified, the analyses of AEs will be descriptive in nature. All analyses of AEs will be based on the number of subjects with AEs and NOT on the number of AEs. BI standards as presented in “Analysis and Presentation of Adverse Event Data from Clinical Trials – Display Template” [BI-KMED-BDS-HTG-0041] ([11](#)) and [BI-KMED-BDS-HTG-0066] ([12](#)) will be applied.

The analysis of AEs will be based on the concept of treatment emergent AEs. That means that all AEs will be assigned to ‘screening’, ‘on-treatment’ or ‘follow-up’ phases as defined in [Section 6.1](#). The ‘on-treatment’ and ‘follow-up’ AEs will be analysed based on actual treatments, as defined in [Table 6.1: 1](#).

According to the clinical study protocol, adverse events of special interest (AESI) will be analysed:

Section 5.2.6.1.4 of the CTP:

The following are considered as AESIs:

- Hepatic injury
A hepatic injury is defined by the following alterations of hepatic laboratory parameters:
 - o *An elevation of AST (aspartate transaminase) and/or ALT (alanine transaminase) ≥ 3 -fold ULN combined with an elevation of total bilirubin ≥ 2 -fold ULN measured in the same blood sample, or*
 - o *Aminotransferase (ALT, and/or AST) elevations ≥ 10 fold ULN*

These lab findings constitute a hepatic injury alert and the subjects showing these lab abnormalities need to be followed up according to the ‘DILI checklist’ provided in the ISF. In case of clinical symptoms of hepatic injury (icterus, unexplained encephalopathy, unexplained coagulopathy, right upper quadrant abdominal pain, etc.) without lab results (ALT, AST, total bilirubin) available, the Investigator should make sure that these parameters are analysed, if necessary in an unscheduled blood test. Should the results meet the criteria of hepatic injury alert, the procedures described in the DILI checklist should be followed.

According to ICH E3 ([13](#)), in addition to Deaths and serious adverse events, ‘other significant’ AEs need to be listed in the clinical trial report. These will be any non-serious

adverse event that led to an action taken with study drug (e.g. discontinuation or dose reduced or interrupted).

An overall summary of adverse events will be presented.

The frequency of subjects with AEs will be summarised by treatment, primary system organ class (SOC) and preferred term (PT). Separate tables will be provided for subjects with serious AEs, for subjects with drug-related AEs, for subjects with drug-related serious adverse events and for subjects with AESIs. In addition, the frequency of subjects with AEs will be summarised by treatment, worst intensity, primary system organ class (SOC) and preferred term (PT).

The system organ classes will be sorted by default alphabetically, PTs will be sorted by frequency (within SOC).

In addition, frequencies of subjects with non-serious AEs that had an incidence of > 5% for at least one treatment will be summarised by treatment, primary SOC and PT.

For disclosure of adverse events on EudraCT, additional information not included in a standard AE analysis will be performed. The following three entries will be created:

- Adverse Events per arm for disclosure on EudraCT
- Non-serious Adverse Events for disclosure on EudraCT
- Serious Adverse Events for disclosure on EudraCT

7.8.2 Laboratory data

The analyses of laboratory data will be descriptive in nature and will be based on BI standards [BI-KMED-BDS-HTG-0042] (14). Analyses will be based on normalised values.

Laboratory data will be analysed qualitatively via comparison of laboratory data to their reference ranges. Values outside the reference range as well as values defined as possibly clinically significant will be flagged in the data listings.

Clinically relevant findings in laboratory data will be reported as baseline conditions (at screening) or as AEs (during the trial) if judged clinically relevant by the investigator, and will be analysed as such.

It is the investigator's responsibility to decide whether a lab value is clinically significantly abnormal or not (at the RPM at the latest).

Descriptive statistics of laboratory data including change from baseline will be calculated by planned time point based on the worst value of the subject at that planned time point (or assigned to that planned time point).

7.8.3 Vital signs

Descriptive statistics over time including change from baseline will be performed for vital signs (blood pressure and pulse rate). In the listing the change from baseline will also be displayed.

For vital signs, descriptive statistics will be calculated by planned time point based on the last value of the subject at that planned time point (or assigned to that planned time point). Time courses of vital signs presenting means and standard deviations per time point and treatment group will be provided.

Clinically relevant findings will be reported as baseline conditions (at screening) or as AEs (during the trial) if judged clinically relevant by the investigator, and will be analysed as such.

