#### 5.2.2 Vital signs

Systolic and diastolic blood pressures (BP) as well as pulse rate (PR) or heart rate (heart rate is considered to be equal to pulse rate) will be measured by a blood pressure monitor (e.g., DASH 4000) at the times indicated in the [Flow Chart](#), after subjects have rested for at least 5 min in a supine position. All recordings should be made using the same type of blood pressure recording instrument on the same arm, if possible. If required, vital signs assessment can be repeated.

In addition, oral body temperature may be measured at any time at the discretion of the investigator. These measurements will not be recorded in the eCRF.

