6.7 BASELINE, TIME WINDOWS AND CALCULATED VISITS

The baseline value is defined as the last measurement before drug administration in each treatment period.

Section 6.1 of the CTP:

Exact times of measurements outside the permitted time windows will be documented. The acceptable time windows for screening, the end of trial examination, and measurements and assessments scheduled to occur 'before' trial medication administration in the morning of Day 1 are provided in the CTP Flow Chart.

If not stated otherwise in the CTP Flow Chart, the general acceptable deviation from the scheduled time for vital signs, ECG, and laboratory tests will be ± 30 min.

The acceptable deviations from the nominal urine sampling time points for urinalysis are:

- The pre-dose urine sample will be the first void of the day or a sample collected ≤ 3 h before dosing*
- Post-dose urine samples will be taken ± 2 h from the nominal urine sampling time*

Adherence to time windows will be checked via the consistency check listings at the RPM.

Unscheduled measurements of laboratory data and vital signs data will be assumed to be repeat measurements of the most recent scheduled measurement (e.g. for follow-up or confirmation of a particular value). Therefore, unscheduled measurements will be assigned to the planned time point of the previous scheduled measurement.

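### Vital-sign summaries can show a late unscheduled reading at too early a nominal time, because SAP 6.7 sets no limit on how late a repeat may be

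*SAP*

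**What the plan says.** Two SAP rules act together.

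- **Assignment (SAP 6.7).** "Unscheduled measurements of laboratory data and vital signs data will be assumed to be repeat measurements of the most recent scheduled measurement". It follows that "unscheduled measurements will be assigned to the planned time point of the previous scheduled measurement". No maximum gap is given. The ±30 min tolerance in the same section applies to scheduled measurements.
- **Selection (SAP 7.8.3).** Descriptive statistics by planned time point, including change from baseline, are "based on the last value of the subject at that planned time point (or assigned to that planned time point").

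The same paragraph of 7.8.3 adds the figures: "Time courses of vital signs presenting means and standard deviations per time point and treatment group will be provided". It does not say which value they use. The SAP history table shows that the figures were added in version 2.

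Protocol 5.2.2 sets neither a trigger nor a time limit for repeats: "If required, vital signs assessment can be repeated".

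Two other provisions bear on the point. SAP 7 states that "The individual values of all subjects will be listed, sorted by treatment sequence, subject number and visit", and 7.8.3 says of the vital-sign listing that "In the listing the change from baseline will also be displayed". SAP 7.8.3 also sends findings that the investigator judges clinically relevant to the adverse-event analysis.

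**The concern.** Calling an unscheduled reading a repeat is sound when it is taken a few minutes after the scheduled one. It is not sound for a reading taken many hours later for another reason, and the Flow Charts leave long stretches in which that could happen. Under the two rules such a reading does two things: it takes the place of a valid scheduled value, and it appears at a time when it was not taken.

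The gap from 4 h to 24 h matters most, because it contains the evening dose of the reference treatment. A reading taken after that dose would be displayed at a time before it.

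At stake are the time axis and the change from baseline in the vital-sign tables and figures. These support the safety and tolerability objective in Protocol 7.1. No pharmacokinetic endpoint is involved.

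**Working it through.** The documents give no figure on this point, so there is none to reproduce. The check sets the rules against the schedule and then sizes a single replacement.

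**Inputs**
- Scheduled vital signs in each period, from both protocol Flow Charts: pre-dose (nominally −1.5 h), 2, 4, 24 and 72 h. Screening and end-of-trial readings lie outside the periods.
- Reference doses at 0 and 12 h (reference Flow Chart); test treatments at 0 h only.
- Subjects analysed: 7 in cohort 1 and 14 in cohort 2 (SAP 4).
- Baseline: last measurement before dosing in each period (SAP 6.7).
- Difference between the replaced and the replacing reading: not in the documents. I assume 20 to 40 mmHg for illustration.

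**Step 1: how far a reading can be misplaced.** The upper bound is the next scheduled time minus the scheduled time.

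| Slot receiving the reading | Next scheduled | Upper bound |
|---|---|---|
| pre-dose (−1.5 h) | 2 h | 3.5 h |
| 2 h | 4 h | 2 h |
| 4 h | 24 h | 20 h |
| 24 h | 72 h | 48 h |

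The bounds are approached but not reached. Against the 0.5 h tolerance for scheduled readings, the last two are 20 / 0.5 = 40 and 48 / 0.5 = 96 times as wide.

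**Step 2: an example under the reference treatment.** Take an unscheduled reading at 16 h, which is 16 − 12 = 4 h after the evening dose. SAP 6.7 assigns it to 4 h, and 7.8.3 selects it as the last value there. It is shown 16 − 4 = 12 h too early, at a nominal time 12 − 4 = 8 h before the evening dose. The real 4 h value leaves the summary.

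**Step 3: the pre-dose slot.** Read literally, a reading between dosing and 2 h goes to the pre-dose time point. The baseline definition still excludes it, because it follows dosing. The pre-dose row of the table and the baseline could then disagree for the same subject.

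**Step 4: effect on a mean.** If one subject's value changes by d and all n subjects contribute, the mean shifts by d / n. The mean change from baseline shifts by the same amount, since baseline is unchanged.

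- n = 7: 20 / 7 = 2.9 mmHg; 40 / 7 = 5.7 mmHg.
- n = 14: 20 / 14 = 1.4 mmHg; 40 / 14 = 2.9 mmHg.

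**Step 5: a contrast within the protocol.** For ECGs, Protocol 5.2.4 separates repeats made for quality reasons, which are the ones analysed, from additional unscheduled recordings made for safety. SAP 6.7 draws no such line for vital signs.

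**The case against.** The case for leaving the rule alone is substantial. It is pre-specified and its assumption is stated openly: an unscheduled value follows up or confirms the latest scheduled one. On that assumption the last value is a natural choice, and replacing a faulty reading with a valid repeat is good practice. Baseline is also a last value, so post-dose and baseline readings are selected alike. The rule is the same for every treatment, so a spurious treatment difference would need unscheduled readings to differ between treatments in number or level. Nothing in the documents shows that a late unscheduled reading occurred. SAP 4 also reports that development has stopped, so no later part of the trial depends on these means.

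All of this stands for prompt repeats, and it limits the size of the point. It does not rescue the assumption for a reading taken hours later, where the rule gives a wrong time and discards a valid value.

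A reader might infer more, and the documents do not support it:

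- **That abnormal values disappear.** They leave the summaries only. Individual values are listed, and clinically relevant findings become adverse events.
- **That safety rests on these summaries alone.** Protocol 2.2.2.2 also names adverse events, laboratory tests and ECG.
- **That the summaries are biased toward normal.** This needs repeats to follow mainly abnormal readings, and the documents do not say what prompts one. A share of readings above a threshold is not a planned output for vital signs either.
- **That the laboratory rule should change as well.** SAP 7.8.2 summarises laboratory data "based on the worst value of the subject at that planned time point". Choosing between last and worst value for a prompt repeat is a trade-off, and the difference between the two domains is not an error in itself.

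**Conclusion.** The point holds in a narrow form and is minor. Applied as written, SAP 6.7 and 7.8.3 give a wrong result for any unscheduled vital-sign reading that is not a prompt repeat. This is a consequence of a stated rule and not a matter of missing detail.

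The misplacement bounds follow from the Flow Charts alone. The shifts in mmHg rest on an assumed difference for one subject and on all 7 or 14 subjects contributing at that time point. How often such readings occurred is unknown; if there were none, the outputs are unaffected. That the figures share the fault is a fair inference from their place in 7.8.3, not something the SAP states.

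**What to change.** In SAP 6.7 and 7.8.3, for vital signs:

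1. Assign an unscheduled reading to a planned time point only if it is a repeat within the ±30 min window of that time point.
2. Otherwise keep the scheduled value for by-time-point statistics, change from baseline and the time-course figures, and say explicitly that the figures use the same value as the tables.
3. Show later unscheduled readings in the listings at their actual time.
4. Keep the baseline consistent with this rule: select it from pre-dose readings in the Flow Chart's pre-dose window, and never place a post-dose reading in the pre-dose slot.
5. Optionally, add the worst on-treatment value per treatment, including unscheduled readings, with the direction defined for each parameter.

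The assignment sentence in 6.7 covers laboratory and vital-sign data together, so the new wording should single out vital signs. The worst-value rule in 7.8.2 can stay as it is.

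The cost is a few lines of SAP text and a changed record-selection flag, with no new data. The small downside is a departure from the sponsor's default display.
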